## **7.2. Confidentiality and Disclosure of Data**

All subjects will sign a HIPAA-compliant authorization form containing the mandated core elements and requirements before participation in this clinical study. The sponsor and designees affirm and uphold the principle of the subject's right to protection against invasion of privacy. Throughout this study, a subject's source data will only be linked to the sponsor's electronic data capture system database or documentation via a unique identification number. As permitted by all applicable laws and regulations, limited subject attributes such as gender, age or date of birth, and subject initials may be used to verify the subject and accuracy of the subject's unique identification number.

To comply with ICH Guidelines for GCP and to verify compliance with this protocol, the sponsor requires that the investigator allow review of the subject's original medical records (source data or documents) by the study monitor, representatives from any regulatory authority (e.g., FDA), the sponsor's designated auditors, and the appropriate IRB. These medical records will include, but will not be limited to, clinical laboratory test result reports, ECG reports, admission and discharge summaries for hospital admissions occurring during a subject's study participation, and autopsy reports. Access to a subject's original medical records requires the specific authorization of the subject as part of the informed consent process.

Copies of any subject source documents that are provided to the sponsor must have certain personally identifiable information removed (i.e., subject name, address, and other identifier fields not collected in the subject's eCRF).

Data will be maintained and backed up in the electronic data capture system. All access to the data is protected by username and password, and each staff member and all sponsor staff will have separate access that requires a separate username and password. Access is only given to site staff and requested sponsor staff who have completed the appropriate training.

### **7.3. Subject Consent**

Written informed consent in compliance with 45 CFR 46 will be obtained from each subject before entering the study or performing any unusual or nonroutine procedure that involves risk to the subject. An informed consent template may be provided by the sponsor to the study clinic. If any institution-specific modifications to study-related procedures are proposed or made by the study clinic, the consent should be reviewed by the sponsor or its designee or both before IRB submission. Once reviewed, the consent will be submitted by the investigator to the IRB for review and approval before the start of the study. If the informed consent form is revised during the course of the study, all active participating subjects must sign the revised form.

Before enrollment, each prospective subject will be given a full explanation of the study and be allowed to read the approved informed consent form. The informed consent process will be performed by a clinical research nurse in a private room. The subject will be given unlimited time to ask questions regarding study participation, and each subject will be questioned to ensure their understanding. Once the investigator is assured that the subject understands the implications of participating in the study, the subject will be asked to give consent to participate in the study by signing the informed consent form.

The investigator will provide a copy of the signed informed consent form to the subject. The original form will be maintained in the subject's medical records at the site.

### **7.4. Data Collection**

Full details of procedures for data collection and handling will be documented in the data management plan, which is initiated with the final protocol receipt. The data management plan is a changing document that evolves over the course of the study and is finalized by database lock.

### **7.5. Publications**

No information related to or generated by this study will be released to the public until it has been reviewed by the sponsor. The sponsor shall own intellectual rights for the data. Authorship on publications will be determined by standard journal requirements.

## **8. Study Management**

### **8.1. Release of Study Drug to the Study Clinic**

Before the study drug can be released to the study clinic, the following documents will be collected from the study clinic by the clinical research organization, retained in the trial master file, and a study drug shipment approval form will be completed by the clinical research organization:

- Protocol signature page signed by the investigator
- IRB approval of the protocol and informed consent form and IRB membership list
- Completed Form FDA 1572, curriculum vitae, and medical licenses from each investigator
- Financial disclosure and debarment certification from each investigator
- Executed contract with investigator and study clinic

### **8.2. Monitoring**

The sponsor or its designee will monitor the study to ensure that it is being conducted according to the protocol, GCP standards, and applicable region-specific requirements, and to ensure that study initiation, conduct, and closure are adequate. The investigators and the study clinic staff will be expected to cooperate fully with the study monitors and personnel or agents of the sponsor, and be available during monitoring visits to answer questions sufficiently and to provide any missing information. The investigators and their institutions will permit direct access to source data/documents for study-related monitoring activities, audits, IRB reviews, and regulatory inspections.

During any on-site visits, the study monitor will:

- Check and assess the progress of the study
- Review all informed consent forms
- Review study data collected
- Conduct source document verification
- Identify any issues and address their resolution
- Verify that the facility remains acceptable
- Conduct study drug accountability

These monitoring activities will be done in order to verify that the:

- Data are authentic, accurate, and complete.
- The safety and rights of the subjects are being protected.

- The study is being conducted in accordance with the currently approved protocol (including any amendments), GCP, and all applicable regulatory requirements.

In addition, the sponsor, designated auditors, and government inspectors must be allowed access to eCRFs, source documents, and other study files that may be required to evaluate the conduct of the study.

### **8.3. Management of Protocol Amendments and Deviations**

#### **8.3.1 Modification of the Protocol**

Any changes in this research activity, except those necessary to remove an apparent immediate hazard to the subject, must be submitted to the sponsor or designee and reviewed and approved by the local IRB before implementation. Amendments to the protocol must be submitted in writing to the investigator's IRB for approval before subjects are enrolled into an amended protocol.

#### **8.3.2 Protocol Violations and Deviations**

Any significant protocol deviations that the investigator or study clinic staff believes are of major importance (e.g., incorrect randomizations, subject enrolled but not eligible) should be reported to the sponsor and the investigator's IRB as soon as possible.

Significant protocol deviations may include the following:

- Deviations from the inclusion/exclusion criteria that may affect subject safety
- Deviations (omission or delay) of safety monitoring procedures
- Deviations in the administration of the study drug
- Deviations in obtaining informed consent

All subjects who are enrolled and receive the study drug, regardless of whether they have a major protocol violation, must continue to be followed for safety for all follow-up study visits.

## Table of Abbreviation

Abbreviation	Definition
AUC 0-inf	area under the concentration-time curve from time zero to infinity
AUC 0-t	area under the concentration-time curve from time zero to last on-study sample
AUEC 0-t	area under the effect curve from time zero to last on-study sample
AUEC	area under the effect curve
pAUEC 0-t	percentage area under the effect curve from time zero to last on-study sample
CL/F	apparent clearance
C max	maximum observed concentration
EC 50	the exposure that gives-half maximal response, model parameter
ED 50	the dose that gives-half maximal response, model parameter
E max,exp	maximum PD response, model parameter – concentration analysis
E max,dose	maximum PD response, model parameter – dose analysis
FDA	Food and Drug Administration
IFN β-1a	interferon beta-1a (Avonex®)
K el	elimination rate
mg	milligram
ΔMxA dec, max	maximum increase from baseline in MxA protein
ΔNeopterin dec, max	maximum increase from baseline in neopterin
PD	pharmacodynamic
pegIFN β-1a	pegylated interferon beta-1a (Plegridy®)
PK	pharmacokinetic
RNA	ribonucleic acid
SC	subcutaneously
SD	standard deviation
T max	time of maximum concentration (C max )
t 1/2	terminal half-life
V/F	apparent volume of distribution

## Change Log

Version	Section	Changes
2	5	Added that ‘Subjects who did not complete their treatment (referred to as early termination subjects) will not be included in PK and PD parameter summary calculations.’
2	7.3.1, 7.3.2	The descriptive summary for PD parameters is changed from geometric mean to mean. Changes in PD parameter from baseline for placebo and low doses may have negative values and would not allow for calculation of geometric mean. Text describing the primary, secondary, and exploratory PD parameter was updated for clarity.
2	General	Typographical changes included throughout

## **1. Introduction**

This document outlines the proposed statistical methods for data analysis on data collected from Protocol ‘SCR-008: Pharmacodynamic Biomarkers to Support Biosimilar Development: Clinical Study 3 (IFN- $\beta$  Products – Avonex and Plegridy)’.

## **2. Study Objectives**

### **2.1. Primary Objective**

The primary objective of this study is to report clinical trial operating characteristics for future clinical pharmacology pharmacokinetics (PK) and pharmacodynamics (PD) similarity studies using the different biomarker-based approaches.

### **2.2. Secondary Objectives**

The secondary objectives of this study are:

1. To determine the values and variability of PK and PD parameters at three dose levels (i.e., low, intermediate, and high doses) for interferon beta-1a (Avonex®, IFN  $\beta$ -1a) and pegylated interferon beta-1a (Plegridy®, pegIFN  $\beta$ -1a).
2. Explore PK/PD relationships using appropriate models for IFN  $\beta$ -1a and pegIFN  $\beta$ -1a.

### **2.3. Exploratory Objective**

The exploratory objectives of this study are:

1. To evaluate the utility of circulating proteins and small RNAs as potential PD biomarkers.
2. To inform analytical approaches and experimental designs needed for identifying exploratory proteomic- and small RNA-based PD biomarkers in plasma.

## **3. Study Overview**

### **3.1. Study Design**

This is a randomized, double-blind, placebo-controlled, single-dose, parallel arm, pilot study. Healthy subjects will be randomized to one of three dose groups (low, intermediate, and high) for each drug (IFN  $\beta$ -1a and pegIFN  $\beta$ -1a) or placebo (See Table 1). The study will be conducted at one center in the United States (Spaulding Clinical Research unit in West Bend, Wisconsin).

Subjects randomized to Treatment Groups A, B, and C will stay in-house for the duration of the study and will be discharged on Day 7. Subjects randomized to Treatment Groups D, E, F, and G will stay-in house until Day 10 and return for the Day 14 assessment. Each treatment group should include equal representation of male and female subjects.

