After the consent process is complete, demographic data, medical history, and concomitant medications will be recorded. A physical examination will be performed by a study team member. Clinical laboratory tests (hematology, serum chemistry, and urinalysis) will be performed. Female subjects must have a negative pregnancy test result. Screening tests will be performed within 21 days of and no later than 2 days before Day 1.

Results of all screening tests will be evaluated by the study clinician/investigator against the inclusion/exclusion criteria to confirm subject eligibility. At check-in, eligibility criteria will be reviewed, any changes in medical history (including concomitant medications) will be documented, vital sign

measurements and a 12-lead electrocardiogram (ECG) will be performed, clinical laboratory, drug and alcohol, and pregnancy tests (for females) will be performed, an intravenous (IV) catheter may be inserted into the subject's forearm region for blood collection (if needed), study drug will be administered, and blood samples will be collected per protocol.

U.S. Food and Drug Administration (FDA) will prepare the randomization schedule. Subjects will enter the study clinic for check-in procedures (Day -1), the day before study drug administration on Day 1. Avonex will be administered intramuscularly and Plegridy will be administered subcutaneously. Placebo will be administered either subcutaneously or intramuscularly to match study drug.

Subjects will be discharged from the study after completion of all study procedures. If a subject discontinues from the study prematurely, all procedures scheduled for the end of the study will be performed. Meal timing and components, activity levels, and general conditions in the study clinic will be as similar as possible on the treatment days.

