## 5. Investigational Plan

### 5.1. Study Design

This is a randomized, placebo-controlled, single-dose, parallel arm study. Healthy subjects will be randomized to three dose groups (low, intermediate, and high) of each drug (interferon beta-1a [Avonex] and peginterferon beta-1a [Plegridy]) or placebo (see Table 5-1).

Subjects will report to the study site for screening assessments from days -21 to -2 and then will return to the site on day -1 for baseline assessments. Prior to and following study drug or placebo administration on day 1, they will undergo assessments as described in Table 9-1. Subjects randomized to Treatment Groups A-C will stay in house for the duration of the study and will be discharged on Day 7. Subjects randomized to Treatment Groups D-G will stay in house for the duration of the study and will be discharged on Day 14. Each treatment group should include equal representation of male and female subjects.

Depending on the treatment arm, subjects will have up to a maximum of 20 PK and PD blood draws and additional study procedures as outlined in the schedule of events.

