### **5.1.2 Dosing Schedule**

- Treatment Group A: Avonex 7.5 µg, IM
- Treatment Group B: Avonex 15 µg, IM
- Treatment Group C: Avonex 30 µg, IM
- Treatment Group D: Plegridy 31.25 µg, SC
- Treatment Group E: Plegridy 62.5 µg, SC
- Treatment Group F: Plegridy 125 µg, SC
- Treatment Group G: Placebo (6 subjects receive IM and 6 subjects receive SC)

Subjects randomized to Treatment Groups A-C will be discharged on Day 7, while subjects randomized to Treatment Groups D-G will be discharged on Day 14. If a subject discontinues from the study prematurely, all procedures scheduled for discharge Day (i.e., Day 7 or Day 14) will be performed.

Safety will be evaluated in terms of AEs, clinical laboratory results (hematology, serum chemistry, and urinalysis), vital sign measurements (blood pressure, heart rate, respiratory rate, and oral body temperature), safety ECG results, and physical examination findings (see Table 9-1).

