### **5.6.3 Study Periods**

This is a randomized, placebo-controlled, single-dose, parallel arm study. Healthy subjects will be randomized to three dose groups (low, intermediate, and high) of each drug (Avonex or Plegridy) or placebo. Subjects randomized to the Avonex Treatment Groups (A-C) will be discharged on Day 7, while subjects randomized to the Plegridy or placebo Treatment Groups (D-G) will be discharged on Day 14.

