relapsing-remitting disease, and active secondary progressive disease, in adults. PLEGRIDY (peginterferon beta-1a) is an interferon beta-1a to which a single, linear 20,000 dalton (Da) methoxy poly(ethyleneglycol)-O-2-methylpropionaldehyde molecule is covalently attached to the alpha amino group of the N-terminal amino acid residue. The molecular mass of PLEGRIDY is approximately 44,000 Da, consistent with the mass of the protein (approximately 20,000 Da), the carbohydrate moieties (approximately 2,500 Da), and the attached poly(ethylene glycol). However, because of the extended and flexible nature of the attached poly(ethylene glycol) chain, the apparent mass of PLEGRIDY in solution is greater than 300,000 Da. The more than 10-fold increase in apparent mass of PLEGRIDY compared to interferon beta-1a has been shown to contribute to the reduced clearance in vivo. PLEGRIDY is available as a single-dose prefilled pen or single-dose prefilled syringe. PLEGRIDY PEN is composed of an autoinjector that surrounds a prefilled glass syringe containing 0.5 mL of a sterile solution in water for injection of 63, 94, or 125 micrograms of peginterferon beta-1a, 15.8 mg of L-arginine HCl, 0.79 mg of sodium acetate trihydrate, 0.25 mg of glacial acetic acid, and 0.025 mg of polysorbate 20. The pH is approximately 4.8. A prefilled syringe of PLEGRIDY for subcutaneous injection contains 0.5 mL of a sterile solution in water for injection of 63, 94, or 125 micrograms of peginterferon beta-1a, 15.8 mg of L-arginine HCl, 0.79 mg of sodium acetate trihydrate, 0.25 mg of glacial acetic acid, and 0.025 mg of polysorbate 20. The pH is approximately 4.8.

Subjects administered placebo will received either a placebo intramuscular injection or placebo subcutaneous injection. A placebo intramuscular injection of equal volume and comparable pH to the diluent for high dose interferon beta-1a will be injected into upper arm intramuscularly for 6 subjects in the placebo treatment arm. A placebo subcutaneous injection of equal volume and comparable pH to the diluent for high dose peginterferon beta-1a will be injected into the upper arm subcutaneously for 6 subjects in the placebo treatment arm.

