### **5.8.6 Blinding**

The pharmacist (and designated staff member responsible for confirmation of study drug dose) will be unblinded to subject treatment assignment; however, the pharmacist will not perform any study procedures other than study drug preparation and dispensing.

Subjects and staff will be blinded to treatment assignment during confinement, but route of administration will not be blinded. The blind will be maintained through a randomization schedule held by the dispensing pharmacist. Subjects and staff will be informed of a subject's end of study day when discharged from confinement. Subjects and staff will not be informed of the specific treatment arm assignment. The clinical research nurse will administer the subcutaneous study drug in unit dose containers that are not transparent.

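### SAP 3.1 calls the trial double-blind, but open route and arm-dependent stay reveal active versus placebo for intramuscular subjects from the planned Day 7 discharge

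*SAP*

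**What the plan says.** The SAP's design statement (3.1) is unqualified: "This is a randomized, double-blind, placebo-controlled, single-dose, parallel arm, pilot study." The Protocol's counterpart (5.1) makes no such claim: "This is a randomized, placebo-controlled, single-dose, parallel arm study."

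Protocol 5.8.6 describes the masking: "Subjects and staff will be blinded to treatment assignment during confinement, but route of administration will not be blinded." It adds that subjects and staff learn the "end of study day when discharged from confinement".

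Route follows drug. The Protocol synopsis says "Avonex will be administered intramuscularly and Plegridy will be administered subcutaneously". Protocol 5.1.2 and 5.8.1 split placebo Group G into 6 intramuscular and 6 subcutaneous subjects.

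Stay follows treatment group. Protocol 5.6.3 says "Subjects randomized to the Avonex Treatment Groups (A-C) will be discharged on Day 7"; Groups D-G leave on Day 14. SAP 3.1 gives the same Day 7 for A-C, but keeps D-G in house to Day 10 with a return on Day 14.

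On safety, Protocol 5.7.4.1.2 runs adverse event recording from consent to discharge or early termination. Severity and causality are investigator judgements (5.7.4.1.3 and 5.7.4.1.4). SAP 7.7.1 tabulates treatment-emergent events by seriousness, severity, relationship and treatment, with no common time window.

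**The concern.** Open route tells everyone which drug a subject might have received: Avonex or placebo if intramuscular, Plegridy or placebo if subcutaneous. What is left to mask is active versus placebo within route, and dose within drug. For intramuscular subjects the schedule undoes the first of these, because active and placebo leave on different days.

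The judgements exposed are the subjective ones. The top causality category in Protocol 5.7.4.1.4 depends partly on whether the event is a recognised reaction to the product or predictable from its pharmacology. An investigator who knows that a subject had placebo would rate relatedness differently. The tables in SAP 7.7.1 also set Avonex groups observed to Day 7 beside a placebo group observed for longer. If the label passes from the SAP into the report, readers will credit these tables with more protection than they have.

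**Working it through.** The check is a cross-tabulation of planned subjects by route, stay and treatment. No power or error-rate figure enters it.

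**Inputs.** Groups A-F have 12 subjects each and G has 12 (Protocol Table 5-1). A-C are intramuscular, D-F subcutaneous, and G is 6 and 6 (Protocol 5.1.2). A-C leave on Day 7 (both documents). D-G stay to Day 14 (Protocol 5.6.3) or to Day 10 with a Day 14 return (SAP 3.1).

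**Planned size.** 6 × 12 + 12 = 84, and 84 + 14 replacements = 98. Both agree with the documents.

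**Intramuscular subjects.** 3 × 12 + 6 = 42.
- Before the Day 7 discharge: placebo share 6/42 = 14.3%.
- Discharged on schedule on Day 7: placebo share 0/36 = 0%, so all are Avonex.
- Remaining after Day 7: placebo share 6/6 = 100%.

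The result is the same under the Protocol stay and the SAP stay.

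**Subcutaneous subjects.** 3 × 12 + 6 = 42. All follow the longer schedule, so the placebo share is 6/42 = 14.3% both before and after Day 7. Stay length tells nothing.

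**Dose.** A, B and C share one schedule, and so do D, E and F. Stay length does not reveal dose level within a drug.

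**Extent.** Active-versus-placebo status is revealed for 42 of 84 planned subjects (50%): 36 by leaving and 6 by remaining. The 6 are 6/12 = 50% of the placebo arm.

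**Sensitivity to extended stays.** Protocol 5.6.1.1 provides for a longer clinic stay for safety reasons. The documents give no expected number, so assume that k active intramuscular subjects are kept past Day 7. The placebo share among intramuscular subjects still in house is then 6/(6 + k):
- k = 0: 100%
- k = 1: 6/7 = 86%
- k = 2: 6/8 = 75%
- k = 3: 6/9 = 67%

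**Follow-up.** Since recording ends at discharge, planned observation runs to Day 7 in A-C and to Day 14 in G under the Protocol. Under the SAP, G leaves the clinic on Day 10 and returns on Day 14.

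One further conflict bears on the inputs. A sentence in Protocol 5.1.1 has every study drug given subcutaneously, against the synopsis, 5.1.2, 5.8.1 and SAP Attachment B. The tabulation uses the assignment that those four places share; the sentence must be reconciled with them.

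**The case against.** The strongest reply is that this concerns one word. The Protocol never calls the trial double-blind and openly says that route is not masked. The primary endpoint is a neopterin assay, and planned Avonex sampling ends on Day 7 (Protocol 5.7.1.1, SAP Attachment A), so knowledge gained then can do little to it. Safety is not a listed endpoint, and SAP 7.7.1 is descriptive. Because recording in A-C stops at Day 7 discharge, no planned intramuscular active observation remains for unmasked judgement to be set against. What is left is events arising in 6 subjects about a week after one placebo injection.

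Most of that stands, and it keeps the point minor. It also means that a Day 7 summary should supplement the full table, not replace it. It does not rescue the label, or the Protocol's statement that masking holds throughout confinement. Withholding the end-of-study day until discharge does not help, because anyone who knows the schedule can see that a subject is still in house.

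A reader might also infer that injection volume breaks the blind earlier. The Protocol does describe "A placebo intramuscular injection of equal volume and comparable pH to the diluent for high dose interferon beta-1a", and lower doses are measured down from the same syringe. But the documents do not say whether lower doses are made up to volume. The opaque containers in 5.8.6 are mentioned only for subcutaneous drug. No conclusion about volume follows either way, and none is drawn here.

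**Conclusion.** The point holds as a minor mismatch between the SAP's label and the design. Under planned stays, the 6 intramuscular placebo subjects are identifiable after Day 7, and the 36 Avonex subjects are identifiable when they leave on schedule. This rests on the intramuscular and subcutaneous assignment in Protocol 5.1.2 and on subjects following the planned schedule.

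Two stronger readings are not supported:
- A reader might infer that every intramuscular subject in house after Day 7 is certainly placebo. Safety-extended stays make that untrue in principle, and an intramuscular subject who leaves early could be either.
- A reader might infer that all relatedness ratings in half the placebo arm are unmasked. Only judgements made after Day 7 are exposed, and the documents do not say when causality is rated.

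The primary neopterin result is unlikely to be affected. The practical consequences are an overstated blinding claim and safety tables that compare unequal follow-up.

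**What to change.** **SAP 3.1.** Replace the double-blind label with wording such as: *Subjects and staff are intended to be masked to active versus placebo and to dose within route. Route is open. Under planned stays, active versus placebo is revealed for intramuscular subjects from the Day 7 discharge.* Align Protocol 5.8.6 with this, since its statement about masking during confinement cannot hold for intramuscular placebo after Day 7.

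**SAP 7.7.1.** Keep the full summary of treatment-emergent events. Add a summary of incidence, severity and relationship restricted to onset through Day 7, for comparing the Avonex groups with placebo. This equalises follow-up and covers the period when the blind is intended to hold. An event with onset by Day 7 could still be rated later, so the table limits the problem without removing it.

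**Reconcile.** The stay of Groups D-G differs between the Protocol and SAP 3.1, and the route sentence in Protocol 5.1.1 conflicts with the rest. Both need to be resolved; no change of discharge day or administration is proposed here.

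The cost is one extra table, a few sentences, and a weaker blinding claim in the report.
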